## **SUMMARY OF CHANGES**

[figure not shown]
Compare v3.0 to v3.1

1. [name] replaces [name] as Protocol Director and IND Sponsor.
  - a. Cover page updated
  - b. Section 7 updated with name of IND Sponsor
  - c. Appendix A updated

## PROTOCOL SYNOPSIS

TITLE	Phase II Study Of Epcadostat (INCB024360) With Pembrolizumab (MK-3475) In Metastatic Or Unresectable Gastroesophageal Junction And Gastric Adenocarcinoma Requiring Paired Biopsies
STUDY PHASE	II
INDICATION	Metastatic or unresectable gastroesophageal junction or gastric adenocarcinoma having progressed on at least one line of prior therapy for metastatic disease
INVESTIGATIONAL PRODUCTS	Epcadostat (INCB024360) Pembrolizumab (MK 3475)
PRIMARY OBJECTIVE(S)	To assess 6-month progression free survival (PFS)
SECONDARY OBJECTIVE(S)	To evaluate response rate (RR), overall survival (OS), and the safety and tolerability of Epcadostat (INCB024360) in combination with Pembrolizumab (MK3475) by CTCAE v5
TREATMENT SUMMARY	Non-randomized, single arm, open-label Oral Epcadostat at 300 mg twice daily + Intravenous Pembrolizumab at 200 mg every 3 weeks for up to 24 months
SAMPLE SIZE	30 patients undergoing pre- and on-treatment tumor biopsies
STATISTICAL CONSIDERATIONS	This is a single-stage study for the doublet epcadostat and pembrolizumab. A 6-month PFS of 20% was observed using single agent pembrolizumab and is the basis for the null hypothesis of the present study [1]. We will enroll 30 patients over 18 months and follow patients for at least 6 months. This design has 80% power to reject a 20% PFS rate, if the true PFS is 39%. Calculation based on binomial probabilities with a one-sided significance of 10%.

**SCHEMA**

**Key Inclusion Criteria:**

- Adenocarcinoma of the distal esophagus, gastroesophageal junction or stomach, including patients with HER2 + disease
- Patients must have metastatic or unresectable disease, including those with HER2+ disease having received Herceptin (trastuzumab)
- Must have progressed on at least one line of prior therapy for metastatic disease
- ECOG performance status 0 or 1
- Presence of measurable disease per RECIST v1.1, assessed within 4 weeks prior to study entry
- Tumor deemed amenable to biopsy by core or endoscopic biopsy
- Patient willing to undergo two newly-obtained biopsies - before and on-treatment, provided the procedure is not deemed high-risk and is clinically feasible

**Primary Outcome:** To assess 6-month progression free survival (PFS)

## LIST OF ABBREVIATIONS AND DEFINITION OF TERMS

ADA	Antidrug antibody
ADL	Activities of daily living
AE	Adverse event
AHSCT	Autologous hematopoietic stem cell transplant
ALP	Alkaline phosphatase
ALT	Alanine aminotransferase
ANOVA	Analysis of variance
aPTT	Activated partial thromboplastin time
AST	Aspartate aminotransferase
BID	Twice daily
BMI	Body mass index
BSA	Body surface area
CBC	Complete blood count
CFR	Code of Federal Regulations
CI	Confidence interval
C MAX	Maximum concentration of drug
CNS	Central nervous system
CR	Complete response
CRF	Case report/Record form
CT	Computed tomography
CTCAE	Common Terminology Criteria for Adverse Events
CTLA-4	Cytotoxic T-lymphocyte-associated antigen-4
DC	Dendritic cell
D LCO	Diffuse lung capacity for carbon monoxide
DLT	Dose Limiting Toxicity
DSMB	Data Safety Monitoring Board
ECG	Electrocardiogram
ECOG	Eastern Cooperative Oncology Group
eCRF	Electronic case report form
EOT	End of treatment
ER	Estrogen receptor
FDA	Food and Drug Administration
FDG	Fluorodeoxyglucose
FIGO	International Federation of Gynecology and Obstetrics
FISH	Fluorescence in situ hybridization
GCP	Good Clinical Practice
GI	Gastrointestinal
GLP	Good Laboratory Practices
GU	Genitourinary
HBV	Hepatitis B virus
HCV	Hepatitis C virus

HER2	Human epidermal growth factor receptor 2
Hgb	Hemoglobin
HIPAA	Health Insurance Portability and Accountability Act of 1996
HIV	Human Immunodeficiency Virus
HPF	High-power field
HPV	Human papillomavirus
HTN	Hypertensions
ICF	Informed consent form
ICH	International Conference on Harmonisation
IDO1	Indoleamine 2,3 dioxygenase-1
IEC	Independent ethics committee
Ig	Immunoglobulin
IHC	Immunohistochemistry
IN	Investigator Notification
INR	International normalized ratio
irAE	Immune-related adverse event
IRB	Institutional Review Board
irRC	Immune-related response criteria
ITT	Intent to treat
IV	Intravenous
LFT	Liver function (chemistry) test
LH	Luteinizing hormone
LLN	Lower limit of normal
MAOI	Monoamine oxidase inhibitors
MedDRA	Medical Dictionary for Regulatory Activities
MRI	Magnetic resonance imaging
MTD	Maximum tolerated dose
NSAID	Nonsteroidal anti-inflammatory drug
NSCLC	Non-small cell lung cancer
ORR	Objective response rate
OS	Overall survival
PAD	Pharmacologically active dose
PD	Pharmacodynamic or progressive disease
PD-1	Programmed death receptor 1
PD-L1	Programmed death ligand 1
PET	Positron emission tomography
PFS	Progression free survival
PgR	Progesterone receptor
PK	Pharmacokinetic
PLT	Platelet
PR	Partial response
PT	Prothrombin time
RECIST v1.1	Response Evaluation Criteria In Solid Tumors Version 1.1
RP2D	Recommended Phase 2 dose

RR	Response rate
SAE	Serious adverse event
SD	Stable disease
SNRI	Serotonin/norepinephrine reuptake inhibitors
SS	Serotonin syndrome
SSRI	Serotonin reuptake inhibitors
SUSAR	Suspected unexpected serious adverse reaction
Treg	Regulatory T cell
TTP	Time to progression
ULN	Upper limit of normal
UNK	Unknown
WBC	White blood cell
WHO	World Health Organization

## **1. OBJECTIVES**

### **1.1. Primary Objective**

- 1.1.1. To assess 6-month progression free survival (PFS)

### **1.2. Secondary Objectives**

- 1.2.1. To evaluate objective response rate (RR) by RECIST v1.1 and irRC
- 1.2.2. To evaluate overall survival (OS)
- 1.2.3. To assess the safety and tolerability of epacadostat in combination with pembrolizumab by NCI CTCAE v5

### **1.3. Exploratory Objectives**

- 1.3.1. To determine the responder rate defined as the proportion of subjects with an increased ratio of CD8+ to Treg cells in on-treatment compared with pre-treatment biopsies
- 1.3.2. To identify putative immunologic biomarkers of tumor response

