#### **2.5. Correlative Studies Background and Rationale**

Blood and tissue will be collected for future correlative studies and stored at Stanford. For further information, see Section 9.0

- Blood: Plasma, and PBMC will be collected every three weeks for correlative studies.
- Tissue: Pre and on-treatment (day 42 ± 5 days) tissue biopsies will be collected for correlative studies.

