### 3.3. Exclusion Criteria

The subject must be excluded from participating in the study if the subject:

- 3.3.1. Is currently participating and receiving study therapy or has participated in a study of an investigational agent and received study therapy or used an investigational device within 4 weeks of the first planned dose of treatment.
- 3.3.2. Has known hypersensitivity to pembrolizumab and/or Epacadostat or any of their excipients.
- 3.3.3. Has had a prior anti-cancer monoclonal antibody (mAb) within 4 weeks prior to study Day 1 or who has not recovered (i.e.,  $\leq$  Grade 1 or to baseline) from adverse events due to agents administered more than 4 weeks earlier. Note that denosumab for treatment for bone metastases is allowed.
- 3.3.4. Has had prior chemotherapy, targeted small molecule therapy, or radiation therapy within 2 weeks prior to study day 1 or who has not recovered (i.e.,  $\leq$  Grade 1 or to baseline) from adverse events due to a previously administered agent.
- *Note:* Subjects with  $\leq$  Grade 2 neuropathy are an exception to this criterion and may qualify for the study.

- *Note:* If subject received major surgery, they must have recovered adequately from surgery prior to starting therapy.
- 3.3.5. Have been treated on any Merck-sponsored pembrolizumab-containing gastric cancer pivotal trial will require prior authorization by Merck in order to enroll in this study.
- 3.3.6. Has had prior therapy with IDO-inhibitors
- 3.3.7. Has active autoimmune disease that has required systemic treatment in the past 2 years (i.e. with use of disease modifying agents, corticosteroids or immunosuppressive drugs). Replacement therapy (e.g., thyroxine, insulin, or physiologic corticosteroid replacement therapy for adrenal or pituitary insufficiency, etc.) is not considered a form of systemic treatment.
- 3.3.8. Has known history of, or any evidence of active, non-infectious pneumonitis
- 3.3.9. Has received a live vaccine within 30 days of planned start of study therapy.
- Note: Seasonal influenza vaccines for injection are generally inactivated flu vaccines and are allowed; however, intranasal influenza vaccines (e.g., Flu-Mist®) are live attenuated vaccines, and are not allowed.*

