#### 4.9.3. **Tumor Biopsy**

Fresh tumor biopsies (defined as a biopsy specimen taken since completion of the most recent prior chemotherapy regimen) will be required at baseline and on treatment of the same lesion (day 42  $\pm$  5 days). Patients are not required to have PD-1 expression testing for enrollment on the study. All sites of disease that are amenable to biopsy are allowable per protocol. Measurable lesions that are the only site of measurability per RECIST v1.1 cannot be biopsied due to obstruction of measurement. Additionally, previously irradiated lesions cannot be biopsied due to potential for necrotic and nonviable tissue.

Standard techniques will be used for all biopsies, which may include CT, ultrasound, or endoscope depending on site of biopsiable lesion. The sample should be obtained as core or endoscopic. Fine needle aspirations (FNA) samples are acceptable. The total number of core biopsies obtained should be approximately 6-15, with an average of 10.

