## **8. CORRELATIVE/SPECIAL STUDIES**

Blood and tissue will be collected during the context of the study for future correlative studies including organoids (tissue) and immune markers (blood). Section 9 outlines the frequency of the testing being done and then being stored with the intent to analyze in the future.

For the context of this particular protocol, we will only be collecting and storing blood, serum, plasma, and tissue that could be used for the indicated testing in the future.

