### **8.2. Tissue Samples**

Pre-treatment and on-treatment biopsies are to be collected on patients when safe and feasible.

Details and methods for obtaining, processing, and shipping the fresh tumor biopsy are as follows:

- 6-15 (average 10) core biopsies measuring at least 4mm, if possible 10mm will be obtained from an accessible and safe primary or metastatic tumor site
- When feasible, all core samples should be obtained from the same lesion/location at the appropriate time point
- When feasible, 16-18 gauge needles should be used to obtain core samples. FNA samples are acceptable
- Samples should contain at minimum 20% tumor viability as measured by adequate number of living cells based on H&E slide
- Specimens will be collected/stored in FFPE or as a single cell suspension via the Correlatives Sciences Unit SOP.

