13 Tumor molecular profiling can be performed on archived tissue or newly obtained during the study participation

14 If a coumadin-based anticoagulant is given, INR should be monitored weekly for the first 4 weeks after initiation of therapy and again upon discontinuing epacadostat.

15 TSH required at all day 1 visits, T3 and fT4 only required if TSH is abnormal or patient is symptomatic.

16 For women of childbearing potential, a serum pregnancy test is required at screening but must be within 3 days before first dose of study treatment. Pregnancy tests (serum or urine) should be repeated as needed if required by institutional regulations.

17 CEA and CA19-9 will be checked at baseline on C1D1 prior to Pembrolizumab and Epacadostat and, if elevated, followed every 9 weeks during therapy.

18 Before pembrolizumab dose every 3 weeks

19 Fresh tumor biopsy will be collected pre-treatment (between day -14 to day 0) and on treatment (day 42 ± 5 days). For additional reference go to section 4.9.3 and 8.2

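### Exploratory objective 1.3.1 counts any rise in the CD8+/Treg ratio as a response with no reference rate; its status and the baseline biopsy timing also need reconciling.

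*Combined protocol and SAP*

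**What the plan says.** Objective 1.3.1 (Section 1.3, Exploratory Objectives) is to determine a responder rate, defined as "the proportion of subjects with an increased ratio of CD8+ to Treg cells in on-treatment compared with pre-treatment biopsies". Objective 1.3.2 is to identify candidate immunologic biomarkers of response. No minimum change, allowance for measurement variability or comparison rate is given. Sections 12.1 to 12.4 cover PFS, response rate, OS, safety, laboratory data and sample size, and contain no analysis for either objective.

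The synopsis gives the sample size as "30 patients undergoing pre- and on-treatment tumor biopsies". Section 8.2 is softer: "Pre-treatment and on-treatment biopsies are to be collected on patients when safe and feasible".

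On use of the samples, Section 8 says that under this protocol "we will only be collecting and storing blood, serum, plasma, and tissue that could be used for the indicated testing in the future". Section 2.5 agrees: "Blood and tissue will be collected for future correlative studies and stored at Stanford". Section 8 mentions organoids for tissue and immune markers for blood, and names no tissue CD8/Treg assay.

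On the baseline specimen, Section 4.9.3 describes a fresh biopsy as one "defined as a biopsy specimen taken since completion of the most recent prior chemotherapy regimen", with no day limit. Footnote 19 of the Schedule of Events says "Fresh tumor biopsy will be collected pre-treatment (between day -14 to day 0" and refers the reader back to 4.9.3 and 8.2.

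**The concern.** A ratio measured twice in small tumour samples will differ between samples even if nothing has changed, and under 1.3.1 any upward difference makes a responder. Without a stated reference, a rate of 50% or 60% could be read as pharmacodynamic activity when chance alone gives about that figure. Reducing each pair to up or down also discards the size of the change, which matters when there are at most 30 pairs.

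Two inconsistencies add to this. The objectives promise a result, while Section 8 confines this protocol to storage. And a baseline specimen that predates day -14 but follows chemotherapy passes 4.9.3 and fails footnote 19. Any treatment or elapsed time between an older specimen and day 1 would be mixed into the change that 1.3.1 measures.

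The objective is exploratory, but the title says the study requires paired biopsies and inclusion criteria 3.2.9 and 3.2.10 build them into eligibility, so the comparison should be interpretable.

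**Working it through.** **The plan's own figure.** The only design figure is for the primary endpoint (Section 12.1): N = 30, 20% versus 39%, one-sided 10%, 80% power. The exact binomial rule of at least 10/30 has level P(X ≥ 10 | 0.20) = 0.061 and power P(X ≥ 10 | 0.39) = 0.793; at least 9/30 has level 0.129, above 10%. The figure reproduces and does not depend on the biopsy objective. No rate, power or precision is stated for 1.3.1, so nothing there can be reproduced.

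**Chance responder rate.** Input: 30 pairs (synopsis). If pre- and on-treatment ratios are exchangeable under no drug effect, P(rise) = (1 − P(tie))/2.
- No ties: 0.50. Expected responders 30 × 0.50 = 15, SD √(30 × 0.25) = 2.7.
- 5% to 20% ties (assumed): 47.5% down to 40%.
- Non-drug trend shifting the median log change by −0.25 to +0.25 SD (assumed, normal): Φ(−0.25) = 0.40 to Φ(0.25) = 0.60.

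**What an observed rate would show.**
- 15/30: exact (Clopper-Pearson) 95% CI 31.3% to 68.7%.
- 18/30 (60%): under a chance rate of 0.5, P(X ≥ 18) = 0.18.
- At the plan's one-sided 10%, P(X ≥ 19) = 0.1002 just misses and P(X ≥ 20) = 0.049. So 20/30 (67%) would be needed to exceed 50%.

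**Cost of dichotomising.** Assumed, since the documents give nothing here: paired log-ratio changes normal with mean 0.5 SD, two-sided 5%. Then P(rise) = Φ(0.5) = 0.691. Sign-test power is exact; signed-rank power is simulated.

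| Pairs | Sign-test rejection region (actual level) | Sign-test power | Signed-rank power |
|---|---|---|---|
| 30 | ≤ 9 or ≥ 21 (4.3%) | 55% | about 73–74% |
| 20 | ≤ 5 or ≥ 15 (4.1%) | 38% | about 55% |

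The 20-pair row is an illustration. The documents give no expected number of evaluable pairs, but Section 8.2 makes collection conditional.

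**Baseline timing side by side.** Exclusion 3.3.4 rules out a patient who "Has had prior chemotherapy, targeted small molecule therapy, or radiation therapy within 2 weeks prior to study day 1". A day -14 to 0 specimen will therefore generally also follow the last chemotherapy and satisfy 4.9.3. The reverse does not hold: a post-chemotherapy specimen from before day -14 satisfies 4.9.3 only.

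**The case against.** The objective is exploratory, no test or decision hangs on it, and a descriptive proportion is legitimate. That stands, and it limits the weight of the point. It does not remove the need for a reference value against which to read the proportion.

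The power figures rest on a shift and a significance level that the plan does not state. That also stands; they illustrate a loss and are not properties of this trial. The gap does not come from the choice of level: at one-sided 10% with 30 pairs it is 69% for the sign test and about 91% for signed-rank.

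A reader might infer that exactly half of patients respond with no drug effect and that a 50% to 60% rate means nothing. The documents do not support that. Half is not stated anywhere, depends on exchangeability without ties, and 60% would be weak evidence rather than none.

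A reader might also infer that the trial cannot deliver the biopsy result. Section 8 stores the samples with later analysis in view, so the analysis is deferred. What conflicts is the wording of the objectives and of Section 8.

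On timing, 4.9.3 can be read as defining fresh tissue and footnote 19 as adding a window, so that both apply. The Schema asks for newly obtained biopsies, and Section 4.3.1 limits screening to 28 days with consent before study procedures. Older specimens could therefore enter only as tissue taken before consent. This narrows the problem, but no passage says that the rules are cumulative.

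Finally, the log-change analysis does not solve attribution: a non-drug trend biases it as well.

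**Conclusion.** The point holds as an improvement to an exploratory analysis and a consistency correction. As defined, the responder rate has a chance level of about 50% (roughly 40% to 60% under the ties or trends assumed above), so an observed 50% to 60% is compatible with no activity. Under the assumed 0.5 SD shift, using only the direction of change costs about 17 to 19 percentage points of power at 20 to 30 pairs. The mismatch between objectives 1.3.1 and 1.3.2 and Section 8 is explicit. The two baseline timings overlap but are not the same. Neither the primary PFS analysis nor any secondary endpoint is affected.

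**What to change.** 1. Summarise 1.3.1 as the within-patient change in log(CD8+/Treg), with an estimate, 95% CI and Wilcoxon signed-rank test. If the responder rate is kept, show it with its exact CI against about 50%. State the number of evaluable pairs, and state that without a control arm a non-drug trend cannot be separated from a drug effect.
2. Reconcile 1.3.1 and 1.3.2 with Section 8: either state that the tissue assay and its analysis belong to this protocol, or label these objectives as deferred to future work.
3. Reconcile the baseline timing in 4.9.3 and footnote 19. Which rule applies is for the investigators to settle. In the analysis, flag baseline specimens taken before day -14 and repeat the analysis without them.

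Cost: a little more analysis work and a protocol clarification, with no new tissue or procedures. Bringing the assay into this protocol goes beyond analysis wording, because the assay must then be specified; labelling the objectives as deferred avoids that.

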## **2. BACKGROUND**

### **2.1. Study Disease**

Gastroesophageal junction (GEJ) and gastric adenocarcinomas constitute a major health problem worldwide. Gastric cancer is the fourth most prevalent malignancy and the second leading cause of cancer death worldwide [2]. In the United States, an estimated 24,590 cases of gastric cancer will be diagnosed and 10,720 patients will die from this disease in 2015 [3]. Esophageal cancer is overall less common, but the incidence of adenocarcinoma of the esophagus, GEJ and gastric cardia has risen faster than any other malignancy in the last 25 years in the United States and other Western countries [4]. Although treatment for patients with unresectable or metastatic disease remains palliative, chemotherapy improves survival and quality of life when compared to best supportive care [5]. With standard treatment options, the progression free survival (PFS) for unresectable or metastatic disease is 4 to 6 months and median overall survival (OS) is 7 to 10

months. Recent trials in the second-line setting have shown median PFS is 2-3 months and median OS is 3-5 months [6, 7].

Data are emerging to suggest a role for checkpoint modulators in GEJ/gastric cancers and include antibodies against PD-L1 (atezolizumab)[8] and CTLA-4 (tremelimumab) [9]. Most recently, the KEYNOTE-012 study (NCT01848834), a multicenter, open-label, study of intravenous pembrolizumab included a cohort of 39 patients with PD-L1 expressing advanced gastric cancer. The majority of patients received  $\geq 2$  prior therapies. The 6-month PFS was 26%; median PFS was 1.9 months. 6-month OS was 66%, median OS was 11.4 months. 22% of patients achieved a partial response (PR) and 14% achieved stable disease as measured by RECIST v1.1 and central review.[1]

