An immunohistochemistry (IHC) assay was used to evaluate PD-L1 expression in subject's baseline tumor biopsies. A modified H-score scoring system of PD-L1 expression was established for NSCLC by analyzing tumor specimens from resected NSCLC specimens. This scoring system was then applied to the samples from this portion of the study. Pretreatment tumor PD-L1 expression was a statistically significant predictor of response. In subjects with evaluable tumor PD-L1 expression, the majority of confirmed responses by RECIST v1.1 (and irRC) occurred in subjects with tumors strongly positive for PD-L1. A total of 35 subjects from this study had evaluable tumor samples and a clinical response assessed. Seven of the 35 subjects had a clinical response (20%) by investigator-assessed irRC. Six responders (26%) were observed among the 23 subjects whose tumors expressed PD-L1. Of note, these 6 responders clustered at the higher end of the modified H-score. Six of 9 subjects (67%) whose tumors expressed PD-L1 to an extent above the preliminary cut point had a clinical response. Only 1 response was noted among the 12 subjects whose tumors did not express PD-L1.

A training set comprising approximately 140 tumor samples and their associated clinical outcome data were used to assess an optimal cut point for PD-L1 positivity. An optimal PD-L1 cut point was identified by receiver operator characteristic curve analyses and by considering clinical implications of false-positive and false-negative results. Cut points were identified based on a proportions score method of IHC analysis, with the tumors expressing at or greater than the

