## 12. STATISTICS CONSIDERATIONS

### 12.1. Statistical Design

This is a single-stage study for the doublet epacadostat and pembrolizumab. A 6-month PFS of 20% was observed using single agent pembrolizumab and is the basis for the null hypothesis of the present study (Bang, abstract 4001, GI ASCO 2015). We will enroll 30 patients over 18 months and follow patients for at least 6 months. This design has 80% power to reject a 20% PFS rate, if the true PFS is 39%. Calculation based on binomial probabilities with a one-sided significance of 10%. The level of significance for the primary endpoint in Phase 2 is one-sided 10%, which is deemed acceptable for a proof-of-concept study.

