## 12.2. Safety Analyses

### 12.2.1. Analysis Plan

The analysis will be done on the intent to treat population and patients who drop out will be censored at the point of last follow up.

The primary endpoint of the study is 6-month Progression-free survival (PFS), which is defined as number of days from the first day of taking study dose to the earlier of death or disease progression by RECIST v1.1 for solid tumors. Median PFS will be estimated using the Kaplan-Meier method.

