#### 12.4. **Sample Size**

We will enroll 30 patients over 18 months and follow patients for at least 6 months.

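### The 20% null is credited to a PD-L1-expressing cohort for which section 2.1 reports 26%, and the plan does not justify it as the pembrolizumab-alone rate in a trial that enrols regardless of PD-L1

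*Combined protocol and SAP*

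**What the plan says.** The Protocol Synopsis states: "A 6-month PFS of 20% was observed using single agent pembrolizumab and is the basis for the null hypothesis of the present study". It cites reference 1, and section 12.1 repeats the statement with the same abstract. Section 12.1 adds "This design has 80% power to reject a 20% PFS rate, if the true PFS is 39" per cent, and "Calculation based on binomial probabilities with a one-sided significance of 10" per cent. Section 12.4 sets the size: "We will enroll 30 patients over 18 months and follow patients for at least 6 months".

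Section 2.1 cites the same reference and says the study "included a cohort of 39 patients with PD-L1 expressing advanced gastric cancer". It reports a 6-month PFS of 26% and says that most patients had received two or more prior therapies. Section 2.3.1 also calls the cohort PD-L1 expressing.

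No criterion in 3.2, 3.3 or Appendix A concerns PD-L1. Section 4.9.3 says: "Patients are not required to have PD-1 expression testing for enrollment on the study" (the text names PD-1, not PD-L1). Criterion 3.2.5 asks for progression on, or intolerance to, at least one prior line for metastatic disease. Section 12 has no analysis by PD-L1 or by prior lines, and no section requires PD-L1 status to be recorded.

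**The concern.** In a single-arm trial the historical rate is the only comparator. To judge whether adding epacadostat improves on pembrolizumab, the null should be the 6-month PFS that pembrolizumab alone would give in patients like those enrolled. Here the source cohort was selected on a marker that the trial ignores.

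The plan's own background gives a reason to think the marker matters. In lung cancer, section 2.3.1 calls PD-L1 a significant predictor of response to pembrolizumab, with 6 of 23 expressers responding; of the others it says "Only 1 response was noted among the 12 subjects whose tumors did not express PD-L1". Prior treatment differs too, and could act in the opposite direction: a less pretreated group may do better on pembrolizumab alone.

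If the null is too high for the enrolled mix, a useful doublet can miss the bar because of case mix. If it is too low, an inactive addition can clear it. The 20% is also not the figure that 2.1 reports for the cited cohort, so the reader cannot tell whether it is a PD-L1-selected rate, a discounted all-comer rate or an error.

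**Working it through.** **Inputs from the documents.** N = 30, null 20%, alternative 39%, one-sided 10%, binomial (12.1, 12.4). The 6-month PFS reported for the cited cohort is 26% (2.1).

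**Step 1: reproduce the plan's figure.** With X ~ Bin(30, p), take the smallest r for which P(X ≥ r | p = 0.20) ≤ 0.10.
- r = 9: alpha 12.9%, too large.
- r = 10: alpha 6.1%; power P(X ≥ 10 | p = 0.39) = 79.3%.

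The stated 80% reproduces, with rejection at 10 or more of 30.

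**Step 2: use the 26% in section 2.1.**
- False-positive rate of the planned rule if pembrolizumab alone gives 26%: P(X ≥ 10 | p = 0.26) = 23.5%.
- Design with a 26% null: r = 11 gives alpha 13.2%, too large; r = 12 gives alpha 6.6%. Power at 39% is then P(X ≥ 12 | p = 0.39) = 52.4%.

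**Step 3: allow for PD-L1 mix.** The documents give neither the PD-L1-positive share nor a PD-L1-negative rate for gastric or GEJ cancer. Assumptions:
- share positive, π: 40-70%;
- pembrolizumab-alone 6-month PFS: 26% in positives (2.1), x = 7-15% in negatives;
- planned effect in both groups, as a constant hazard ratio: ln(0.39)/ln(0.20) = 0.585.

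Formulas:
- pembrolizumab-alone rate in the mix: m = π·0.26 + (1 − π)·x;
- doublet rate: d = π·0.26^0.585 + (1 − π)·x^0.585, where 0.26^0.585 = 0.455;
- type I error P(X ≥ 10 | m) and power P(X ≥ 10 | d).

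| π | x | m | d | Type I error | Power |
|---|---|---|---|---|---|
| 0.4 | 7% | 14.6% | 30.8% | 0.8% | 45% |
| 0.5 | 14% | 20.0% | 38.6% | 6.1% | 78% |
| 0.7 | 15% | 22.7% | 41.7% | 12% | 87% |

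The first and last rows are the extremes of the grid. The middle row shows that 20% can be about right for a mixed population.

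**Step 4: repeat with 20% in positives.** If 20% is instead taken as the PD-L1-positive rate, m is 12.2-18.5%, type I error 0.2-3.8% and power 33-73%. The null is then too high throughout and the test conservative. The direction of the bias depends on which figure is right for the source cohort, and the plan does not settle that.

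**Step 5: what a PD-L1-positive subset could show.** A share of 40-70% of 30 gives 12-21 positives. Exact 95% intervals for observed rates near 39%: 5/12 (42%), 15-72%; 8/21 (38%), 18-62%. Both include 20% and 26%.

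**The case against.** **The power statement is not wrong.** A reader might infer that the stated 80% fails because PD-L1-negative patients are enrolled. It is explicitly conditional on a true rate of 39% and reproduces. Case mix bears on whether 39% is what the planned effect would produce, not on the calculation.

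**20% may already suit an unselected population.** Starting from 26% in expressers, plausible inputs give 20% in the mix with 78% power. This stands as a possibility, but no section says that 20% was derived this way; the synopsis and 12.1 say it was observed.

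**A lower true rate makes the test conservative.** This stands too. A reader might infer that the result could not count for or against epacadostat whatever it shows. If the null is too high, a positive result is stronger evidence, not weaker. Resetting the null and keeping the 19-point gain also preserves power: a null of 18% gives r = 9 and 84% power at 37%; a null of 15% gives r = 8 and 85% at 34%.

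**The PD-L1 effect is borrowed.** The only evidence in the documents is from lung cancer, and the 6/23 versus 1/12 split is small and concerns response, not PFS. Hence the negative rate above is an assumption with a range.

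**A comparison by PD-L1 is not ruled out.** A reader might infer that it could never be made. Section 4.9.3 says only that testing is not needed for enrolment, and section 8.2 has tumour tissue collected and stored. What is missing is a plan to record or use the status.

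**Prior lines overlap.** Criterion 3.2.5 requires at least one line, so heavily pretreated patients are eligible. The difference from the source cohort may be modest.

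**Conclusion.** The concern holds as a gap in justification, and should be addressed. The sole comparator is credited to a PD-L1-selected, mostly heavily pretreated cohort, is applied to PD-L1-unselected patients without argument, and differs from the rate that 2.1 reports for that cohort.

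The firmest part needs no assumption about PD-L1: 20% and 26% are attributed to the same reference and not reconciled. If 26% is the true pembrolizumab-alone rate, the false-positive rate is 23% instead of 6.1%, and a valid 26% null has 52% power at 39%.

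The PD-L1 part rests on assumed shares and rates and on a constant hazard ratio. Under those, type I error is 0.8-12% and power 45-87%. The documents do not support a claim that the null is biased in one known direction, or that the trial is underpowered for that reason.

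**What to change.** 1. In the synopsis and 12.1, reconcile 20% with the 26% in 2.1. State that the source cohort was selected for PD-L1 expression and whether 20% is meant as an all-comer rate, with the reasoning. Restate the rejection rule, alpha and power for the null that is kept.
2. Record PD-L1 status in the eCRF where an existing pathology or molecular profiling result gives it. Prespecify 6-month PFS with an exact confidence interval in PD-L1-expressing patients, beside the overall result, as a descriptive comparison with the reconciled cohort rate.
3. Report 6-month PFS by number of prior lines (1 versus 2 or more). Section 4.3.7.2 already has prior treatments reviewed.

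The cost is wording in two places, one eCRF field and a few descriptive table rows, with no new biopsy. If the reconciled null is 26%, the sponsor must also accept lower power at 39% or revisit the sample size or target. The subset estimates will be imprecise (Step 5). PD-L1 will be missing for some patients, since section 4.9.1.6 does not say that the molecular profiling includes it.
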